3. PATIENT ELIGIBILITY

3.1. Inclusion Criteria

- Diagnosis of one of the following
 - Arms A, B, E, and F only: PMF per the revised World Health Organization (WHO) criteria ([Appendix B](#)),
 - Arms A, B, E, and F only: post-ET/PV MF per the IWG-MRT criteria ([Appendix C](#)).
 - Arm D only: Blast-phase MF defined as the presence of 20% or more blasts in the peripheral blood or bone marrow
 - Arm G only: MDS/MPN or MDS patients with spliceosome mutations including SF3B1, SRSF2 and U2AF1 mutations or ring sideroblasts. Diagnosis of MDS/MPN and MDS is per WHO criteria ([Tefferi and Vardiman 2008](#)). Direct sequencing will be used to confirm the presence or absence of spliceosome mutations.
- Indication for treatment of one of the following:
 - Arms A, B, E and F only: High-risk or Intermediate-2 risk MF (as defined by the Dynamic International Prognostic Scoring System [DIPSS-plus]; [Appendix A](#)).
 - Arm G only: presence of severe anemia defined as hemoglobin of <9 g/dL or other indications for cytoreductive therapy per physician discretion
- Presence of the following:
 - Arms E and G only: spliceosome mutations, including SF3B1, SRSF2 and U2AF1 mutations (by direct sequencing) or ring sideroblasts.
- Absence of the following:
 - Arm F only: spliceosome mutations (by direct sequencing) and ring sideroblasts
- ≥ 18 years of age with life expectancy of ≥ 12 weeks.
- Able to provide informed consent and be willing to sign an informed consent form.
- Eastern Cooperative Oncology Group (ECOG) performance status of 0, 1 or 2 ([Appendix D](#)).

- Evidence for acceptable organ function \leq 14 days of study registration as evidenced by the following:
 - SGOT (AST) \leq 2.5 x upper limit of normal (ULN) (or \leq 5 x ULN if in the investigator's opinion the elevation is due to extramedullary hematopoiesis)
 - SGPT (ALT) \leq 2.5 x upper limit of normal (ULN) (or \leq 5 x ULN if in the investigator's opinion the elevation is due to extramedullary hematopoiesis)
 - Total bilirubin \leq 3.0 mg/dL (or direct bilirubin $<$ 1 mg/dL).
 - Creatinine \leq 3.0 mg/dL.
 - Absolute neutrophil count \geq 1000/ μ L (this requirement not needed for Arm D).
 - Platelet count \geq 50,000/ μ L (this requirement not needed for Arm D).
- Females of childbearing potential must have a negative pregnancy test \leq 7 days prior to registration, unless they are surgically sterile (i.e., hysterectomy), OR postmenopausal (FSH $>$ 30 U/mL).

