11. TREATMENT EVALUATION

11.1. Myelofibrosis

Table 15: Revised International Working Group for Myeloproliferative Neoplasms Research and Treatment (IWG-MRT) and European LeukemiaNet (ELN) response criteria for myelofibrosis.

Response categories	Required criteria (for all response categories, benefit must last for ≥ 12 weeks in order to qualify as a response)
Complete Remission (CR)	
Bone marrow: ¹ Age-adjusted normocellularity; <5% blasts; \leqGrade 1 myelofibrosis², AND
 
Peripheral blood: Hemoglobin ≥ 100 g/L and <UNL; Neutrophil count $\geq 1 \times 10^9$/L and <UNL; Platelet count $\geq 100 \times 10^9$/L and <UNL; <2% immature myeloid cells³, AND
 
Clinical: Resolution of disease symptoms; Spleen and liver not palpable; No evidence of EMH

Partial Remission (PR)	
Peripheral blood: Hemoglobin ≥ 100 g/L and <UNL; Neutrophil count $\geq 1 \times 10^9$/L and <UNL; Platelet count $\geq 100 \times 10^9$/L and <UNL; <2% immature myeloid cells³, AND
 
Clinical: Resolution of disease symptoms; Spleen and liver not palpable; No evidence of EMH, OR
 
Bone marrow: ¹ Age-adjusted normocellularity; <5% blasts; \leqGrade 1 myelofibrosis², AND
 
Peripheral blood: Hemoglobin ≥ 85 but <100 g/L and <UNL; Neutrophil count $\geq 1 \times 10^9$/L and <UNL; Platelet count ≥ 50 but <100 $\times 10^9$/L and <UNL; <2% immature myeloid cells³, AND
 
Clinical: Resolution of disease symptoms; Spleen and liver not palpable; No evidence of EMH

Clinical Improvement (CI)	The achievement of anemia, spleen or symptoms response without progressive disease or increase in severity of anemia, thrombocytopenia or neutropenia ⁴
Anemia response	
Transfusion-independent patients: a ≥ 20 g/L increase in hemoglobin level⁵
 
Transfusion-dependent patients: becoming transfusion-independent⁶

Spleen response ⁷	
A baseline splenomegaly that is palpable at 5-10 cm, below the LCM, becomes not palpable⁸, OR
 
A baseline splenomegaly that is palpable at >10 cm, below the LCM, decreases by $\geq 50\%$⁸
 
A baseline splenomegaly that is palpable at <5 cm, below the LCM, is not eligible for spleen response
 
Confirmation by MRI or CT showing $\geq 35\%$ spleen volume reduction is recommended (but not required)

Response categories	Required criteria (for all response categories, benefit must last for ≥ 12 weeks in order to qualify as a response)

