Progressive disease ⁹	
Appearance of a new splenomegaly that is palpable at least 5 cm below the LCM, OR
 
A $\geq 100\%$ increase in palpable distance, below LCM, for baseline splenomegaly of 5 to 10 cm, OR
 
A 50% increase in palpable distance, below LCM, for baseline splenomegaly of >10 cm, OR
 
Leukemic transformation confirmed by a bone marrow blast count of $\geq 20\%$, OR
 
A peripheral blood blast content of $\geq 20\%$ associated with an absolute blast count of $\geq 1 \times 10^9/L$ that lasts for at least 2 weeks

Stable disease	Belonging to none of the above listed response categories
Relapse	
No longer meeting criteria for at least CI after achieving CR, PR or CI, OR
 
Loss of anemia response persisting for at least one month, OR
 
Loss of spleen response persisting for at least one month

Key: CT = computed tomography; EMH = extramedullary hematopoiesis (no evidence of EMH implies the absence of pathology- or imaging study-proven non-hepatosplenic EMH); LCM = left costal margin; MRI = magnetic resonance imaging; UNL = upper normal limit

¹ Baseline and post-treatment bone marrow slides are to be stained at the same time and interpreted at one sitting by a central review process. Cytogenetic and molecular responses are not required for CR assignment.

² Grading of myelofibrosis is according to the European classification (*Thiele et al. Haematologica 2005;90:1128*). It is underscored that the consensus definition of “a complete remission bone marrow” is to be used only in those patients where all other criteria, including resolution of leukoerythroblastosis, are met. It should also be noted that it was a particularly difficult task for the working group to reach a consensus regarding what represents a complete histological remission.

³ Immature myeloid cells constitute blasts + promyelocytes + myelocytes + metamyelocytes + nucleated red blood cells. In splenectomized patients, $<5\%$ immature myeloid cells is allowed.

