⁴ See table 15 for definitions of anemia response, spleen response and progressive disease. Increase in severity of anemia constitutes the occurrence of new transfusion dependency or a ≥ 20 g/L decrease in hemoglobin level from pre-treatment baseline that lasts for at least 12 weeks. Increase in severity of thrombocytopenia or neutropenia is defined as a 2-grade decline, from pre-treatment baseline, in platelet count or absolute neutrophil count, according to Common Terminology Criteria for Adverse Events (CTCAE) version 4.0. In addition, assignment to clinical improvement (CI) requires a minimum platelet count of $\geq 25,000 \times 10^9/L$ and absolute neutrophil count of $\geq 0.5 \times 10^9/L$.

⁵ Applicable only to patients with baseline hemoglobin of <100 g/L. In patients not meeting the strict criteria for transfusion-dependency at the time of study enrollment (see below), but have received transfusions within the previous month, the pre-transfusion hemoglobin level should be used as the baseline

⁶ Transfusion dependency before study enrollment is defined as transfusions of at least 6 units of packed red blood cells (PRBC), in the 12 weeks prior to study enrollment, for a hemoglobin level of <85 g/L, in the absence of bleeding or treatment-induced anemia. In addition, the most recent transfusion episode must have occurred in the 28 days prior to study enrollment. Response in transfusion dependent patients requires absence of any PRBC transfusions during any consecutive “rolling” 12-week interval during the treatment phase, capped by a hemoglobin level of ≥ 85 g/L.

⁷ In splenectomized patients, palpable hepatomegaly is substituted with the same measurement strategy

⁸ Confirmation of spleen or liver responses by imaging studies is recommended (but not required), where a $\geq 35\%$ reduction in spleen or liver volume, assessed by magnetic resonance imaging (MRI) or computed tomography (CT), is required for confirmation. Furthermore, a $\geq 35\%$ volume reduction in the spleen or liver, by MRI or CT, constitutes a response regardless of what is reported with physical examination.

Symptoms are evaluated by the Myeloproliferative Neoplasm Symptom Assessment Form total symptom score (MPN-SAF TSS). The MPN-SAF TSS is assessed by the patients themselves and includes fatigue, concentration,

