early satiety, inactivity, night sweats, itching, bone pain, abdominal discomfort, weight loss, and fevers. Scoring is from 0 (absent/as good as it can be) to 10 (worst imaginable/as bad as it can be) for each item. The MPN-SAF TSS is the summation of all the individual scores (0-to-100 scale). Symptoms response requires $\geq 50\%$ reduction in the MPN-SAF TSS.

⁹ Confirmation by MRI or CT is recommended (but not required) to confirm progressive disease assignment for splenomegaly, where a $\geq 25\%$ increase in spleen volume from baseline is required for confirmation. Baseline values for both physical examination and imaging studies refer to pre-treatment baseline and not to post-treatment measurements.

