16.3. Primary Outcome Analyses(to be evaluated in each arm independently)

Definition: The primary endpoint in each arm of this trial is the overall response rate. For Arms A, B, C, E, and F overall response is defined to be a CI, PR, or CR noted as the objective status according to the IWG-MRT consensus criteria for MF. Response in Arm G is defined as HI, PR or CR according to the IWG criteria for MDS ([Cheson et al. 2006](#)). Response in Arm D is defined by a durable (2 months or more) decrease in peripheral blood and bone marrow blast percentage to less than 5%. All patients meeting the eligibility criteria who have signed a consent form and have begun treatment will be evaluable for overall response.

Estimation: The proportion of successes will be estimated in each arm by the number of successes divided by the total number of evaluable patients. Ninety-five percent Clopper-Pearson exact binomial confidence intervals for the true success proportion will be calculated.

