4.2. Primary Efficacy Endpoint

4.2.1. Definition

The primary endpoint in each arm is the overall response rate. For Arms A, B, E, and F overall response is defined to be a CI, PR, or CR noted as the objective status according to the IWG-MRT consensus criteria for MF. Response in Arm G is defined as HI, PR or CR according to the IWG criteria for MDS (Cheson et al. 2006). Response in Arm D is defined by a durable (2 months or more) decrease in peripheral blood and bone marrow blast percentage to less than 5%. The primary outcome will be the percentage of responses observed in each arm in the eligible analysis set.

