4.3. Major Secondary Endpoints

4.3.1. Definition

Spleen Response

Spleen response is defined as either a minimum 50% reduction in palpable splenomegaly of a spleen that is at least 10 cm at baseline or a spleen that is palpable at less than 10 cm but more than 5 cm at baseline becomes not palpable.

Transfusion Independence

Transfusion dependency is defined by a history of at least 2 units of red blood cell transfusions in the last month or a baseline hemoglobin level of less than 85 g/L that was not associated with clinically overt bleeding. For a transfusion dependent subject, transfusion independence is defined as he/she met either of the following conditions:

- Received no more than 1 unit of red blood cell transfusions in a rolling time interval of 30 days or more.
- Had a hemoglobin level increase over baseline more than 2g/dl if his/her baseline hemoglobin level was less than 85 g/L and received no transfusion.

Time to Response (TTR)

Time to response is defined as the duration from Study Day 1 to the earliest date that a response is first documented. For non-responders, it will be censored at the date of progressive disease/relapse or the date of the last adequate assessment, whichever comes first.

Duration of Response (DoR)

Duration of response is defined for responders as the interval from date of the initial documentation of a response to the date of first documented evidence of disease progression (or relapse for subjects who experience CR). For those subjects who are still without progression/relapse, DoR will be censored at the last adequate assessment.

Overall Survival (OS)

OS is defined as the interval from Study Day 1 to the date of death from any cause. Survival time of living subjects will be censored on the last date a subject is known to be alive or lost to follow-up.

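### The platelet floor for clinical improvement (Protocol Table 15, footnote 4) is printed in a unit that no patient could meet, and the SAP does not say which floor was applied

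*Protocol*

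**What the plan says.** Protocol 16.3 makes overall response the primary endpoint. For the myelofibrosis arms it is a CI, PR or CR, "noted as the objective status according to the IWG-MRT consensus criteria for MF". SAP 4.2.1 does the same for Arms A, B, E and F, with Arm C patients grouped into A or B: "overall response is defined to be a CI, PR, or CR noted as the objective status according to the IWG-MRT consensus criteria". The SAP restates no threshold for any category.

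Table 15 in Protocol 11.1 defines CI as "The achievement of anemia, spleen or symptoms response without progressive disease or increase in severity of anemia, thrombocytopenia or neutropenia". Footnote 4 then adds a count condition: "assignment to clinical improvement (CI) requires a minimum platelet count of" at least 25,000 × 10⁹/L, together with an absolute neutrophil count (ANC) of at least 0.5 × 10⁹/L.

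CI is also used elsewhere. Table 15 defines relapse in part as "No longer meeting criteria for at least CI after achieving CR, PR or CI", and SAP 4.3.1 ends duration of response at relapse for patients who had a CR. Table 3, footnote 13 and Protocol 16.5.1 use CI to decide which patients have a response marrow.

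The symptoms route to CI is described in unnumbered text after footnote 8 of Table 15. It uses a patient-reported score: "The MPN-SAF TSS is the summation of all the individual scores (0-to-100 scale). Symptoms response requires" a fall of at least 50%.

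**The concern.** CI is the lowest category that counts as a response, so its definition fixes the lower edge of the primary endpoint. A threshold that cannot be met is therefore an error in the primary endpoint definition. Whoever assigned CI must have used some other rule, or none, and the documents do not record which. Protocol Section 16 says that the SAP supersedes the protocol's analyses, but the SAP only points back to the criteria.

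The value could matter to individual classifications. Protocol 1.4.1 reports Grade 4 myelosuppression in a subset of patients and says that these same patients went on to respond. It does not name the cell line, but in such a population a blood-count floor could decide whether a patient is a CI.

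**Working it through.** The floor is a printed threshold, so no formula reproduces it. The check is one of units: 1 × 10⁹/L = 1,000/µL.

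**Step 1. The printed value.** 25,000 × 10⁹/L = 25,000 × 1,000/µL = 25,000,000/µL.

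**Step 2. Comparison with the protocol's other platelet figures.**

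| Source | As printed | In × 10⁹/L | Printed CI floor ÷ this value |
|---|---|---|---|
| Table 15, CR | at least 100 × 10⁹/L and below the upper normal limit | 100 | 25,000 / 100 = 250 |
| Table 15, marrow-based PR | 50 to below 100 × 10⁹/L | 50 (lower bound) | 25,000 / 50 = 500 |
| 3.1, entry | at least 50,000/µL | 50 | 25,000 / 50 = 500 |
| Table 11, hold thresholds | below 50, or below 100 with a >75% drop | 50; 100 | 500; 250 |
| Appendix B, diagnosis of essential thrombocythemia | at least 450 × 10⁹/L | 450 | 25,000 / 450 ≈ 56 |

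The entry floor carries the note "this requirement not needed for Arm D". It therefore applies in every arm where CI counts. The last row is a threshold for a disease of high platelet counts, and the printed CI floor is still about 56 times higher.

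**Step 3. The literal consequence.** No patient meets the floor, so the number of CIs is 0 and the response rate becomes (PR + CR) / n. The loss is (number of CIs) / n. The documents give no CI counts, so this cannot be turned into percentage points.

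**Step 4. What the units suggest.** If 25,000 was meant per µL, the floor is 25,000 / 1,000 = 25 × 10⁹/L.
- Against CR: 25 / 100 = 0.25. Against entry: 25 / 50 = 0.5.
- The ANC floor in the same sentence is 0.5 × 10⁹/L, against an entry floor of 1,000/µL = 1.0 × 10⁹/L: 0.5 / 1.0 = 0.5.

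Both count floors would then be half of their entry values. This is a consistency check and does not derive the value; 25 × 10⁹/L is not printed anywhere in either document as the CI floor.

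**Step 5. What is not affected.** The designs in Protocol 16.1 take response rates of 10% and 30% as inputs. Their sample sizes, significance levels and power do not involve the floor.

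**Step 6. Duration of response.** A patient still in CR or PR meets at least CI by holding the higher category. SAP 4.3.1 uses relapse as an end point only after a CR. The literal floor would therefore matter only for a CR patient who slips to CI level, who would be misread as relapsed. The link is real but narrow.

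**The case against.** The strongest reply is that this is a typographical slip with no consequence. Haematologists would read the number as 25,000/µL, accrual closed in January 2014, and the SAP analyses recorded objective status. The SAP restates no CR or PR threshold either, so referring to the criteria is ordinary practice. Much of this stands: the effect on the results is probably nil. But incorporation by reference works only when the text referred to is usable. The CR and PR thresholds are usable as printed, and the CI floor is not.

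A second reply is that 25 × 10⁹/L is an inference. That is right, and the correction should be confirmed against the cited criteria.

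A reader might also infer that the symptom score was never collected, or that the response rate is inflated by symptom-only CIs. The documents support neither reading.
- Table 15's notes name the instrument, its scoring and its threshold, and Table 3 has a response assessment before each infusion in Cycles 1 to 9 at which it could have been recorded. The eCRF is not among the documents.
- No symptom-only CI is shown. SAP 4.3.2, 4.3.3 and 5.3 list spleen response, transfusion independence, transfusions and all laboratory data, so most CIs can be traced to a component. The tracing is approximate, because SAP 4.3.1 defines transfusion dependency differently from Table 15.
- The SAP plans percentages with exact intervals and applies no decision rule, so there is no pass or fail result for such a patient to overturn.

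What remains is that neither Table 3 nor the SAP names the score. Protocol 6.1, item 7 asks for baseline symptoms but points to Section 10.6, which covers post-study adverse events, so it does not supply the instrument.

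**Conclusion.** The platelet floor in Table 15, footnote 4 is wrong as written. It is 250 times the CR floor and 500 times the entry floor, and it would leave CI empty in the primary endpoint of Arms A, B, C, E and F. Neither document gives a usable floor. Confidence in this is high; it assumes only that the typeset footnote carries the figure given here, which is a clean and complete expression.

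A reader might go further and conclude that the reported response rates are wrong. The documents do not support that. If assessors used 25 × 10⁹/L, which is likely, nothing changes. If they used another value or none, the size and direction of the effect cannot be determined from the documents. The symptom score is a minor query and does not establish a defect in the endpoint.

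**What to change.** 1. Correct the unit in Table 15, footnote 4. The protocol's units point to 25,000/µL = 25 × 10⁹/L; the sponsor should confirm this against the cited criteria before the change is made.
2. Add one sentence to SAP 4.2.1 giving the platelet floor actually applied when CI was assigned. If it was not 25 × 10⁹/L, or no floor was applied, say so.
3. As a minor query, state whether MPN-SAF TSS was collected and, if convenient, list CIs by component (anemia, spleen, symptoms).

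The cost is one corrected unit, one or two SAP sentences and an optional listing. There is no new data collection and no change to the primary endpoint, which stays on recorded objective status. The SAP's amendment history shows it as a draft, so the sentence can be added there.

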11.2. MDS

The International Working Group response assessment as reported by [Cheson et al. \(2006\)](#) will be utilized.

Table 16: Definition of Disease Response in MDS:

Category	Response Criteria
Complete Remission (CR)	
Bone marrow: $\leq 5\%$ myeloblasts with normal maturation of all cell lines¹
 
Persistent dysplasia will be noted^{1,2}
 
Peripheral blood³
 
 Hgb ≥ 11 g/dL Platelets $\geq 100 \times 10^9/L$ Neutrophils $\geq 1.0 \times 10^9/L^2$ Blasts 0%
Partial Remission (PR)	
All CR criteria if abnormal before treatment except:
 
Bone marrow blasts decreased by $\geq 50\%$ over pretreatment but still $> 5\%$
 
Cellularity and morphology not relevant

Stable Disease (SD)	Failure to achieve at least PR, but no evidence of progression for > 8 weeks
Failure (FAIL)	Death during treatment or disease progression characterized by worsening of cytopenias, increase in percentage of bone marrow blasts, or progression to a more advanced MDS FAB subtype than pretreatment
Relapse after CR or PR	
At least 1 of the following:
 
 Return to pretreatment bone marrow blast percentage Decrement of $\geq 50\%$ from maximum remission/response levels in granulocytes or platelets Reduction in Hgb concentration by ≥ 1.5 g/dL or transfusion dependence

Category	Response Criteria
Disease Progression (PD)	
For patients with:
 
 Less than 5% blasts: $\geq 50\%$ increase in blasts to $> 5\%$ blasts 5%-10% blasts: $\geq 50\%$ increase to $> 10\%$ blasts 10%-20% blasts: $\geq 50\%$ increase to $> 20\%$ blasts 20%-30% blasts: $\geq 50\%$ increase to $> 30\%$ blasts 
Any of the following:
 
 At least 50% decrement from maximum remission/response in granulocytes or platelets Reduction in Hgb by ≥ 2 g/dL Transfusion dependence

¹ Dysplastic changes should consider the normal range of dysplastic changes (modification).

² Modification to IWG response criteria.

³ In some circumstances, protocol therapy may require the initiation of further treatment (e.g., consolidation, maintenance) before the 4-week period. Such patients can be included in the response category into which they fit at the time the therapy is started. Transient cytopenias during repeated chemotherapy courses should not be considered as interrupting durability of response, as long as they recover to the improved counts of the previous course.

Table 17: Proposed Modified International Working Group Response Criteria for Hematologic Improvement

Hematologic improvement ¹	Response criteria ²
Erythroid response (pretreatment, < 11 g/dL)	Hgb increase by ≥ 1.5 g/dL Relevant reduction of units of RBC transfusions by an absolute number of at least 4 RBC transfusions/8 wk compared with the pretreatment transfusion number in the previous 8 wk. Only RBC transfusions given for a Hgb of ≤ 9.0 g/dL pretreatment will count in the RBC transfusion response evaluation ²
Platelet response (pretreatment, $< 100 \times 10^9$ /L)	Absolute increase of $\geq 30 \times 10^9$ /L for patients starting with $> 20 \times 10^9$ /L platelets Increase from $< 20 \times 10^9$ /L to $> 20 \times 10^9$ /L and by at least 100% ²
Neutrophil response (pretreatment, $< 1.0 \times 10^9$ /L)	At least 100% increase and an absolute increase $> 0.5 \times 10^9$ /L ²
Progression or relapse after HI ³	At least 1 of the following: At least 50% decrement from maximum response levels in granulocytes or platelets Reduction in Hgb by ≥ 1.5 g/dL Transfusion dependence

Note: To convert hemoglobin levels from grams per deciliter to grams per liter, multiply grams per deciliter by 10. Hgb indicates hemoglobin; RBC: red blood cell; HI: hematologic improvement.

¹ Pretreatment counts averages of at least 2 measurements (not influenced by transfusions) ≥ 1 week apart (modification).

² Modification to IWG response criteria.

³ In the absence of another explanation, such as acute infection, repeated courses of chemotherapy (modification), gastrointestinal bleeding, hemolysis, and so forth. It is recommended that the 2 kinds of erythroid and platelet responses be reported overall as well as by the individual response pattern.

